**Principal analysis of the secondary outcome measure:**

All secondary outcome measures will be assessed at 30 days and 90 days and will be analysed using an "intention to treat" analysis. Patients will be contacted to see if they have had an urgent visit (to ED or their PCP). If they describe a relapse (an unscheduled visit for worsening COPD), then we will obtain further information from their medical records and/or treating physician. Those patients who relapse within the first 30 days of the trial will have measurements of oxygenation, airflow obstruction, dyspnea, and quality-of-life done on the day of relapse (either from the family physician or the EDs where they attend). These values will be counted as the last day values for purposes of the analysis (i.e., endpoint analysis, with the last observation carried forward).

Continuous outcome measures including absolute and percent changes in FEV1, oxygen saturation, Transitional Dyspnea Index scores, and changes from Day 1 to Day 30 in the scores of the four components of the Chronic Respiratory Questionnaire will be analysed using either parametric procedures (independent t tests) initially, or with non-parametric methods (Wilcoxon Rank Sum) if the data is not normally distributed. At 90 days, the proportion of patients who achieve

compliance with recommendations (for LAAC, LABA/ICS combinations, and rehabilitation referral), relapse and are hospitalized will be compared using unadjusted  $\chi^2$  tests followed by logistic regression procedures. Survival analyses (log-rank tests followed by Cox proportional hazards modelling) will be used to compare time to relapse.

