After normal working hours(see below), when research staff are not available, patients who are eligible and who have consented to enter the study but have been discharged from the ED, will be contacted by the study coordinator the next morning by phone. Randomization will take place at that time and the appropriate process will take place thereafter. Those patients who are discharged from the ED will receive the outpatient treatment package (by the consenting ED physician) used in the study (Appendix 5) for the medical management of their AECOPD. The outpatient medication package will be readily available in the ED, in a reserved area for the study. This is to ensure that there is no delay in their treatment, as well, that their acute management does not impact the effect of the Lung Attack Alert.

As per the above randomization process, patients will be randomized into either the **control** group or the **intervention** group using a web-based randomization process (Epidemiology Coordinating and Research {EPICORE} Centre, Edmonton, AB; <http://www.epicore.ualberta.ca>).

The **control** group will be discharged from the ED, with the standardized outpatient protocol (Appendix 5) and will be advised to follow up with their PCP. They will be provided with general information regarding COPD in the form of the "Breathworks" program pamphlets established by the Canadian Lung Association. These are readily available in print and online, and they are information guides for patients with COPD. The patients will then be contacted by a research staff member unaware of the allocation of treatment at day 30 and 90 post discharge from the ED to discuss the primary and secondary outcomes (**Appendix 7**).

The **intervention** group will also be advised to follow up with their PCP, along with the standardized outpatient protocol for their acute exacerbation (Appendix

5). They will be provided with general information regarding COPD in the form of the “Breathworks” program. The intervention group will have the Lung Attack Alert form completed by the research study staff. The form will highlight the information already discussed earlier. This will then be faxed to their primary care physician by the study coordinator. The patients will then be contacted by a research staff member unaware of the allocation of treatment at day 30 and 90 post discharge from the ED to discuss the primary and secondary outcomes (**Appendix 7**).

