## **Outcomes**

The **Primary Endpoint** of this study is the rate of follow up of the patient by their primary care provider for review of the acute and chronic management of their COPD and addressing any issues on the Lung Attack Alert, within the first 90 days after discharge from the ED. The study coordinator will contact all patients enrolled on day 30 after admission to the ED to determine if a follow up visit has occurred and if any of the recommendations noted on the Lung Attack Alert have been implemented.

A number of **Secondary Endpoints** will be collected. These include 1) relapse of the AECOPD requiring acute intervention (ED or clinic) within the 90-day study period; 2) admission to the hospital within the 90-day study period; 3) review and adjustment of the management of COPD at day 90 post discharge from the ED 4) Proportion of patients who completed their acute management within the 90-day study period and 5) length of stay within the ED.

The study coordinator will contact the PCP of patients in the intervention group to survey the usefulness of the Lung Attack Alert once the study is complete. This survey will assess the clinical utility of the alert and the ease of use of the information provided in the alert to aid in clinical management.

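### Continuous secondary measures: counting relapse-day readings as last-day values means the result is not a Day-30 change, and the change test leaves the Day-1 value unused as a covariate

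*Combined protocol and SAP*

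**What the plan says.** The section on the principal analysis of the secondary outcome measure has patients who relapse in the first 30 days measured for oxygenation, airflow obstruction, dyspnea and quality of life on the day they relapse. It then states: "These values will be counted as the last day values for purposes of the analysis". It describes this as "endpoint analysis, with the last observation carried forward".

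The same section says "All secondary outcome measures will be assessed at 30 days and 90 days" and gives the CRQ outcome as "changes from Day 1 to Day 30 in the scores of the four components of the Chronic Respiratory Questionnaire". The continuous measures "will be analysed using either parametric procedures (independent t tests) initially", with the Wilcoxon rank sum test if the data are not normal. No covariate is named for them. The regression models in the plan are for binary outcomes and time to relapse.

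Elsewhere, Methods has both groups contacted "at day 30 and 90 post discharge from the ED to discuss the primary and secondary outcomes", and Outcomes says "The study coordinator will contact all patients enrolled on day 30 after admission to the ED". Neither makes an exception for relapse.

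**The concern.** Carrying the last observation forward is a way of handling missing values, but nothing in the text ends follow-up at relapse. A patient who relapses on day 8 is still due to be contacted on day 30. Under the rule, that patient contributes a reading taken during an exacerbation, while a patient without relapse contributes (if measured) a Day-30 reading. The mean difference between arms then blends how many patients relapsed, how early and how severely with how patients were at Day 30. A reader shown a Day 1 to Day 30 change could not tell which of these produced a difference, or hid one. Relapse is already analysed in its own right, by proportions and by time to event.

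The second matter is independent of the first. A change score already needs the Day-1 value. Comparing raw changes without also using that value as a covariate gives up precision in a trial of about 49 evaluable patients per group.

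**Working it through.** **What the plan supplies.** It gives no SD, correlation, relapse rate or detectable difference for these measures, so there is no stated figure to reproduce. The group size of 49 comes from Sample Size Considerations, where it was set for the binary follow-up outcome. Everything else below is assumed. Tests are two-sided at 5%, and SD is 1 at both times unless stated.

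**1. Shift from the relapse rule.** Let d be the difference between arms in the proportion relapsing, and g the gap (in SD) by which the relapse-day value is worse than the same patient's Day-30 value.

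Shift relative to Day-30 status = d × g.

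- Equal relapse, no effect: 0 × g = 0. No bias.
- Relapse 25% against 15%, g = 0.5: 0.10 × 0.5 = 0.05 SD.
- Relapse 25% against 15%, g = 1.0: 0.10 × 1.0 = 0.10 SD.

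With p the relapse proportion in an arm and ρ the Day-1 to Day-30 correlation, the variance of the substituted change in that arm is 2(1 − ρ) + g²p(1 − p). At ρ = 0.5 and g = 1.0 this is 1.1875 (p = 0.25) and 1.1275 (p = 0.15). The standard error is √[(1.1875 + 1.1275)/49] = 0.217. From the noncentral t distribution, a trial with no effect on Day-30 status would reject in 7.4% of cases; with g = 0.5 the figure is 5.7%. Over ρ from 0.3 to 0.7 the range is 5.5% to 8.7%.

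**2. Power under the rule.** For a 0.50 SD effect at ρ = 0.5, observed change has variance 1, standard error √(2/49) = 0.202 and power 68.8%. With equal relapse of 15% to 25% and g of 0.5 to 1.0, power under the rule is 61% to 67% if relapse-day readings carry the full effect. It is 36% to 52% if they carry none of it. The documents do not say which is nearer the truth.

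**3. Using the Day-1 value.** Let k be the Day-30 SD divided by the Day-1 SD.

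- Variance of change: 1 + k² − 2ρk.
- Variance with the Day-1 covariate: k²(1 − ρ²).
- Proportional cut: (1 − ρk)² / (1 + k² − 2ρk), which is never negative.

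| ρ (k = 1) | Change | With covariate | Cut |
|---|---|---|---|
| 0.3 | 1.40 | 0.91 | 35% |
| 0.5 | 1.00 | 0.75 | 25% |
| 0.7 | 0.60 | 0.51 | 15% |

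At ρ = 0.5, power for 0.50 SD rises from 68.8% to 80.8%. With unequal SDs at ρ = 0.5, the cut is 0.0625/1.75 = 4% at k = 1.5 and 0.444/0.778 = 57% at k = 1/1.5. These formulas suit measures recorded at both times. They do not suit the TDI, which is already a transition score.

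**The case against.** The strongest reply is that the rule is pre-specified and, in operation, is a composite: status at relapse or at the last day, whichever comes first. That is a legitimate target and is unbiased for itself. Where the arms truly differ in relapse, the rejection rates above are not false positives for that composite. This stands. What is missing is the label and a reason, and the Day 1 to Day 30 wording points to a different quantity.

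Several stronger readings are tempting, and the documents do not support them.

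- *The rule discards observed Day-30 values.* The text describes contact at Day 30, not a visit at which FEV1 or saturation is measured, and Appendices 6 and 7 were not available for this review. Relapsers may be measured on the relapse day instead of Day 30, in which case nothing is overwritten.
- *Only relapsers have a second reading, so the comparison rests on a handful of patients.* This too depends on the unseen appendices.
- *Relapse will be recorded more often in one arm because the alert promotes primary care visits.* The 30% and 60% figures concern follow-up visits, whereas relapse means an unscheduled visit for worsening disease. Both arms are asked directly by staff whom Methods describes as blinded to allocation (although Outcomes names the coordinator for the Day-30 contact). Reports are checked against records, and two physicians adjudicate independently.
- *The rule extends to Day 90.* It covers relapse in the first 30 days, and the only explicit change window ends at Day 30. Only the general statement about both time points suggests more.

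It is also fair to say that the test on change is valid and that the covariate is a matter of precision, not of bias by design.

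**Conclusion.** The point holds as a minor one, for the continuous measures only. As written, early relapsers are analysed at relapse, so the result should not be reported as a Day-30 change. A reader might infer that the rule makes the trial's comparison invalid or biased. It does not: equal relapse with no effect gives no shift, and an assumed 10-point relapse difference with an assumed gap of 0.5 to 1.0 SD gives only 0.05 to 0.10 SD. The main loss is interpretability. Loss of power could be small or substantial, depending on how far relapse-day readings reflect treatment.

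The gain from the Day-1 covariate is more certain in direction than in size: 15% to 35% of variance with equal SDs and correlations of 0.7 to 0.3, and smaller or larger if the SDs differ. Primary care follow-up and the five secondary endpoints listed under Outcomes are untouched.

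**What to change.** First establish, from Outcomes and Appendices 6 and 7, which of these measures are taken at Day 1 and Day 30 and in whom, and say what last day means. Then:

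- **Day-1 and Day-30 values exist.** Make the main analysis a linear model of the Day-30 value on arm and Day-1 value. For the TDI, analyse the Day-30 score, with baseline dyspnea as covariate if collected.
- **Relapsers also have Day-30 values.** Use those regardless of relapse, and keep the relapse-day substitution as a labelled sensitivity analysis.
- **Relapsers are measured only on the relapse day.** Keep the rule, but name the outcome *status at relapse or Day 30*. Do not make imputation from non-relapsers the main analysis, since it would rest on an assumption that cannot be tested.
- **No Day-30 measurement is planned for all patients.** Report no Day-30 change for that measure.

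The cost is analysis wording and a check of the outcome list; no branch requires a new visit or measurement. The downside is that relapse-day physiology may no longer be the main analysed value, and a measure without a planned Day-30 reading loses its Day-30 result.

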## **Methods**

This study will be a 1 year randomized controlled trial to assess the impact of the “Lung Attack Alert” on rates of follow up by PCP of their patients following presentation to the ED for an AECOPD. The tool being assessed is labeled as the “Lung Attack Alert”(see **Appendix 1**). This is a novel information sheet that is intended for the PCP. The Lung Attack Alert summarizes the following points:

- a) that the PCP’s COPD patient has had a presentation to the ED for an AECOPD but did not require a prolonged hospital admission;
- b) a description of the discharge management from the ED will be provided;
- c) a recommendation to the PCP to follow up with the patient within 1-2 weeks after discharge from the ED;
- d) Care gaps identified in the patients chronic management of COPD based on the Canadian Thoracic Society 2007(updated 2008) guidelines will be highlighted for the PCP to address at the next outpatient follow up

Each Lung Attack Alert will be **individualized** to the patients care gap(s) identified during screening.

This study will enroll consecutive patients who present to the ED at the University of Alberta Hospital and the North East Community Center (both located in urban Edmonton), who present with an AECOPD, but who do not require admission to hospital.

ED physicians or the study coordinator will screen patients who present to the ED with an AECOPD, who have recovered from the acute event and are considered safe for discharge. All patients will receive usual care within the ED prior to screening and entry into the study. This may consist of the use of any or all of the following: oxygen, acute bronchodilators (+/- use of nebulizers or MDI), administration of oral/IV corticosteroids, intravenous fluids, non-invasive ventilation (NIV), oral or intravenous antibiotics as required.

Patients will be screened by either the ED physicians who will notify our study coordinator regarding the eligibility of a patient or directly by the study coordinator. Eligible patients (**Appendix 2**) will be provided with a patient information sheet (**Appendix 3**) outlining the rationale for the study. If the patient is agreeable to participate, a consent form will be signed and witnessed by either the ED physician or study coordinator (**Appendix 4**). To be enrolled into the study patients must satisfy all inclusion and exclusion criteria.

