**Inclusion:**

Appropriately signed and dated informed consent has been obtained

ED patients presenting with an acute exacerbation of COPD requiring treatment in the ED;

Previous physician-diagnosis of COPD (e.g., emphysema, chronic bronchitis or COPD) either previously or within the ED;

Age >40 years of age;

Current or former smokers of more than 10 pack years (number of packs of cigarettes {or pipe and/or cigars} smoked per day X the number of years of smoking);

FEV1/FVC ratio < 0.7 for age, sex and height (either known or determined within the ED);

Patients can read and comprehend English language.

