**Principal analysis of the primary outcome measure:**

The final analysis will be performed on an "intention to treat" basis. Using this approach, patients will be included in the analysis according to the group to which they were randomized. Baseline characteristics in the two treatment arms will be compared using univariate descriptive statistics. The principal analysis of 30-day relapse will be done using an unadjusted  $\chi^2$  comparing the proportion of events in each treatment group. A logistic regression procedure will be employed to adjust raw relapse proportions using significant co-variates (such as patient use of inhaled steroids, current smoking status, etc) which may influence outcomes

We chose the proportion of PCP visits within 30 days as a primary outcome measure rather than survival time to relapse. We believe that it is more relevant to both patients and physicians to know if the enhanced intervention will stimulate a PCP visit rather than examining relapse (which may be affected by age, severity, type of treatment received, smoking status, etc). Therefore, unadjusted  $\chi^2$  followed by logistic regression procedures were chosen over log-rank tests followed by Cox proportional hazards modelling. Both alternative analytic approaches mentioned will still be performed and reported.

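### The 90-day guideline-compliance comparison neither separates nor adjusts for patients who already met the recommendation at entry, which costs power but does not bias the randomised comparison

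*Combined protocol and SAP*

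**What the plan says.** The section on the principal analysis of the secondary outcome measure sets the comparison as "At 90 days, the proportion of patients who achieve" "compliance with recommendations (for LAAC, LABA/ICS combinations, and rehabilitation referral". The same sentence continues that those who "relapse and are hospitalized will be compared using unadjusted" chi-square tests, with logistic regression to follow. The section places all secondary outcomes under intention to treat and names no subset. It lists no covariates for the compliance model.

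The only covariate examples are in the section on the primary outcome measure, where raw relapse proportions are to be adjusted for "significant co-variates (such as patient use of inhaled steroids, current smoking status, etc".

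Under Methods, each Alert is individualised "to the patients care gap(s) identified during screening". The inclusion and exclusion criteria do not require a gap. They admit patients with "Previous physician-diagnosis of COPD (e.g., emphysema, chronic bronchitis or COPD) either previously or within the ED", so some may arrive already on a recommended treatment. The nearest listed secondary endpoint, under Outcomes, is "review and adjustment of the management of COPD at day 90 post discharge from the ED"; the analysis section does not link it to the compliance proportions.

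**The concern.** The Introduction states the belief that highlighting care gaps may move treatment towards the guidelines. The compliance proportions are one of the planned tests of that belief. For an item the patient already has, the Alert has no gap to point out. Such a patient will tend to count as compliant in either arm and so adds noise and little signal.

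Chance differences between arms in prior therapy also enter the unadjusted comparison as noise. At 49 per arm and b = 50%, the standard deviation of the between-arm difference in baseline use is √(2 × 0.5 × 0.5 / 49) = 0.101, or about 10 percentage points. At stake is a null compliance result that reads as failure to close gaps when it partly reflects how many patients had no gap to close.

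**Working it through.** **The plan's own figure.** No sample size is given for compliance. The 49 per group comes from 30% versus 60% PCP follow-up (Sample Size Considerations). Two-sided 5%, 80% power:

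n = [1.960√(2 × 0.45 × 0.55) + 0.842√(0.30 × 0.70 + 0.60 × 0.40)]² / 0.30² = 41.97, or 42 per arm.

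Continuity-corrected: (41.97/4)[1 + √(1 + 4/(41.97 × 0.30))]² = 48.4, or 49 per arm, 98 in total. Allowing 10% attrition, 49/0.9 rounds up to 55 per arm, 110 in total. The stated one-tailed setting gives 33 per arm (40 with the correction), so 98 reproduces only as two-sided with the correction. I therefore use 49 evaluable per arm and a two-sided 5% test below.

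**Dilution.** Let b be the share already meeting an item and staying on it, and uC and uT the uptake among patients with the gap. Each arm's compliance is p = b + (1−b)u, so

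pT − pC = (1−b)(uT − uC).

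**Power.** With p̄ the mean of the two proportions and n per arm,

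power = Φ{[(pT − pC)√n − 1.960√(2p̄(1−p̄))] / √(pC(1−pC) + pT(1−pT))}.

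The documents do not give b, uC or uT. Assume uC = 20% and uT = 50%.

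Worked case, b = 50%:
- All patients, 60% versus 75%, n = 49: (0.15 × 7 − 1.960 × 0.6624)/0.6538 = −0.38, power 35%.
- Gap patients only, 20% versus 50%, n = 24: (0.30 × 4.899 − 1.960 × 0.6745)/0.6403 = 0.23, power 59%.

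| b | All patients, control vs Alert | Difference | Power, 49/arm | Gap patients per arm | Power, gap only |
|---|---|---|---|---|---|
| 10% | 28% vs 55% | 27 points | 78% | 44 | 85% |
| 30% | 44% vs 65% | 21 points | 55% | 34 | 75% |
| 50% | 60% vs 75% | 15 points | 35% | 24 | 59% |
| 70% | 76% vs 85% | 9 points | 20% | 15 | 40% |

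**Other uptake rates.** With 30% versus 60%, power is 67% (all) against 77% (gap only) at b = 20%, 47% against 64% at 40%, 30% against 47% at 60%, and 16% against 26% at 80%. On the plan's one-tailed basis the b = 40% pair is 60% against 76%. With 10% versus 30% at b = 40%, it is 22% against 48% two-sided. At b = 0 the two analyses coincide.

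**Keeping all patients but stratifying on baseline status.** Simulated at 20% versus 50% uptake and b = 50%, power rises from about 35% unadjusted to 60% stratified if everyone already on therapy persists. If 90% persist, it rises from 33% to 46%.

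**The case against.** Several points on the other side are sound.

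- A reader might infer that the comparison is biased. It is not. Under randomisation the all-patient comparison estimates a valid population-level effect, and the test's error rate already allows for chance imbalance in prior therapy.
- A reader might take it as stated that patients already on therapy count as compliant. The plan does not say so. *Achieve* could mean newly achieve, and the appendices on the Alert, baseline data and follow-up contacts, which I did not have, might settle it. The text available leaves it undefined.
- The plan does not stop at an unadjusted test. Logistic regression follows, and the relapse model cites inhaled-steroid use as an example covariate. That could recover part of the loss, but no covariate is named for compliance, and the relapse covariates are tied to significance.
- The Alert may also affect patients without a given gap. It always reports the exacerbation and the ED management and asks for early follow-up, which could influence whether existing therapy continues. A gap-only analysis would miss that, which is why the all-patient analysis should stay in the lead.
- Compliance is not the only test of closing gaps. Secondary endpoint 3 is based on change, the primary endpoint text covers addressing Alert issues, and the day-30 call asks whether recommendations were implemented.
- Every rate is assumed, and dilution will differ by item. Where few patients have the item at entry the loss is modest. Even gap-only power in the table is below 80% from b = 30% upward.

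These points limit the size and the wording of the concern. They do not supply the missing definition or the missing covariate.

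**Conclusion.** The concern holds as a loss of power and an undefined endpoint. As written, the lead compliance test is unadjusted, its numerator and denominator do not distinguish new uptake from existing therapy, and no baseline-therapy covariate is named for the follow-up model. The factor (1−b) is exact if those already on therapy all persist whatever their arm, and approximate otherwise.

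On the assumed 20% versus 50% closure, the power given up ranges from 7 points (85 − 78) at b = 10% to 24 points (59 − 35) at b = 50%. For the stratified all-patient analysis the gain at b = 50% falls from 25 points (60 − 35) to 13 (46 − 33) when persistence is 90%. The documents do not support a reading that the result would be biased, that the Alert can act only on patients with a gap, or that the primary result is affected.

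**What to change.** For each of the three recommendations:

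1. Record gap status (yes or no) before randomisation, in the same way in both arms. For patients randomised by the next-morning call, fix it before the allocation is drawn.
2. State whether compliance at day 90 means being on the item or newly meeting it.
3. Make the lead analysis an all-patient intention-to-treat comparison stratified by, or adjusted for, that baseline status. A Mantel–Haenszel test is convenient, because a stratum in which everyone is compliant then contributes nothing and causes no fitting problem.
4. Also report, by arm, the proportion newly meeting the item among patients with that gap at screening. Because the gap is fixed before allocation, this subset keeps the randomised comparison.

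The cost is mostly wording, since Methods says gaps are identified at screening, but not wholly. Methods describes completing the Alert form only in the intervention group, so the screening gap checklist must also be kept for control patients. The gap-only analysis will have smaller denominators, which differ by item.
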